Throughout hospitalization, food intake of patients is often inadequate, due to reduced appetite and disease impact symptoms, such as pain, nausea, decreased taste and smell (12). Adding further complexity to this problem, nutritional requirements are increased due to illness, treatment and the healing process. As such, it can be challenging to adequately meet the nutritional requirements during the course of hospitalization and rehabilitation. Patients at risk of malnutrition will receive individual counseling by a dietitian, aimed at reaching adequate protein and energy intake. As part of this nutritional counseling, oral nutritional supplements (ONS) (i.e., energy and protein-rich drinks) are advised when habitual oral nutrition remains inadequate (75% of protein and energy requirements) (13). ONS are effective in increasing total energy and protein intake, resulting in less complications and re-admissions, as well as improved body weight and physical functioning (14). Currently available ONS mostly contain animal-based proteins, usually in the form of dairy proteins, ensuring high-quality proteins with regard to digestibility, amino acid composition, and bioavailability.

Recently the Dutch Ministry of Health, Welfare and Sport and the Dutch Federation of University centers signed the Green Deal "Working together on sustainable care" in which they agreed on "Green and climate neutral care" by 2026. One of the five goals is to stimulate "a healthy, varied, more plant-based and sustainable diet" (15). This also includes

meeting criteria for purchasing medical and non-medical nutrition in hospitals for future tenders.

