### 4.3 Exclusion criteria

A potential participant who meets any of the following criteria will be excluded from participation in this study:

- Patients who are or become dependent on tube or parenteral nutrition
- Patients where life-extending therapy is no longer possible
- Unable to follow up study instructions
- Lactose intolerance
- Soy allergy/intolerance
- Vegan diet
- Patients who have used ONS in the past six months

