### **6.4 Summary of known and potential risks and benefits**

There are no potential risks associated with this research. Patients will receive ONS as part of their regular treatment, however, with participating in this study they will be randomized to receive either the plant-based or animal-based ONS. Both types of ONS are already available and used in hospitals. Participating in this study has no specific additional benefit. Generally, the use of ONS is expected to increase the energy and protein intake for patients at risk for malnutrition, which in turn improves nutritional status.

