### **6.5 Description and justification of route of administration and dosage**

The dietitian or nurse will decide the number of bottles the patient needs per day, fully in accordance with usual care. The advice of the dietitian or nurse needs to be at least 2 bottles ONS a day for patients to be eligible to participate in this study. This is based on their nutritional intake observed by the nurse or the dietitian will base this advice on their nutritional requirement at the start of their treatment. 2 bottles of ONS is equal to 600 kcal and 30g protein. This means that there need to be a gap between their intake and requirements of  $\geq 600$  kcal and  $\geq 30$  g protein, in order to advice the ONS. Nutritional requirements will be estimated for protein intake as 1.5-1.9 g/kg fat-free mass (FFM)/d and energy intake WHO formula + surcharge up to 50% according to the Dutch guidelines of malnutrition and the ESPEN guidelines Clinical nutrition in surgery, cancer, and geriatrics (6, 13, 23, 24).

If the patient approves to participate in this study and signed the written IC then the patient will be randomised to one of the 2 groups: plant-based ONS or animal-based ONS.

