### **8.2 Randomisation, blinding and treatment allocation**

Patients will be randomized to either the plant-based ONS or animal-based ONS. Randomisation will be done by Castor EDC database. This system will generate the randomisation performed by stratification for 3 different patient populations: (1) oncology, (2) pulmonary diseases (3) other (including cardiology, cardiothoracic surgery, orthopaedic patients) and for the study location (Radboudumc and Maastricht UMC+). In this way, it will be done independently. Patients can not be blinded in this study since it is

not feasible to cover every bottle the patients drink in those 3 months (i.e. patients will receive already existing products with standard packaging and labelling). Nevertheless, the analyses will be carried out in a blinded manner.

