## 13.2 Synthesis

The overall risk of participation in this study is negligible for patients. Consuming dairy products will form risks for people suffering from lactose intolerance, and consuming soy products will form risks for people suffering from soy allergy / intolerance. Therefore, these people will be excluded from participating in this study. Both types of ONS are medically available and are therefore safe for human consumption. All measuring procedures are completely safe and routinely being performed within the Radboudumc and Maastricht UMC+.

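### The exclusion criteria cover soy allergy and intolerance but, for dairy, only lactose intolerance, so a patient with known milk-protein allergy is eligible for randomisation (low-priority safety wording)

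*Protocol*

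**What the plan says.** Section 4.3 of the protocol lists seven exclusions. Two concern tolerance of a product ingredient, "Lactose intolerance" and "Soy allergy/intolerance", and a third excludes people on a vegan diet. Section 13.2 gives the reasoning for the two ingredient criteria. On the dairy side it states: "Consuming dairy products will form risks for people suffering from lactose intolerance". The matching statement for the plant-based side is wider, since it names allergy as well: "consuming soy products will form risks for people suffering from soy allergy / intolerance". It concludes that these people are to be excluded. The two sections agree with each other.

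The protein source of the control product is not stated. Sections 5.1 and 6.1.2 name the product and give its volume, energy and protein content; section 6.1.2 heads it as animal-based. Section 1 says "Currently available ONS mostly contain animal-based proteins, usually in the form of dairy proteins".

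Under section 11.2 the dietitian checks eligibility against the listed criteria. On the nurse route, the researcher finds patients with supplement advice in the electronic record. Section 13.1(j) cites the strictness of the inclusion and exclusion criteria when it answers whether effects can be managed.

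**The concern.** For soy, the protocol treats allergy and intolerance as separate reasons to exclude. For dairy it names only the intolerance. Lactose intolerance is a reaction to the sugar in milk, whereas milk-protein allergy is an immune reaction to the protein, so the first criterion cannot be read to include the second. The list therefore omits the immune-mediated dairy condition, in a trial where the minimum intake at entry is two bottles a day and the study period is three months.

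What is at stake is a foreseeable and avoidable allergic exposure in a rare patient. It is a matter of participant safety and of complete eligibility wording. It has no bearing on the feasibility endpoints, on the convenience sample of 60 or on any analysis.

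**Working it through.** The protocol gives no figure to reproduce on this point. The check is a reading of the criteria, followed by an illustration of scale.

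**1. Apply the seven exclusions of section 4.3** to a non-vegan patient with known milk-protein allergy who digests lactose normally and is otherwise suitable:

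| Exclusion (paraphrased) | Met? |
|---|---|
| Dependence on tube or parenteral feeding | No |
| No life-extending treatment left | No |
| Cannot follow study instructions | No |
| Lactose intolerance | No, a different condition |
| Soy allergy or intolerance | No |
| Vegan diet | No |
| Supplement use in the previous six months | No |

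None of the seven is met, so the patient is eligible.

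**2. Is the control dairy?** Three statements support the inference: the control is described as animal-based (6.1.2), animal-based supplements usually contain dairy protein (section 1), and dairy consumption is the stated reason for excluding lactose intolerance (13.2). That reason makes little sense unless a study product contains dairy. It remains an inference.

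**3. Chance of allocation and dose.** With 30 per group (4.4), the chance of the control is 30/60 = 1 in 2. At 15 g protein per bottle (5.1) and at least two bottles a day at entry (4.2), the dose is 2 × 15 = 30 g protein a day, as section 6.5 also states.

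**4. Expected number of patients.** The protocol gives no prevalence. Assume, for illustration only, that 0.1% to 1% of otherwise eligible patients have a known milk-protein allergy. Expected number = group size × assumed prevalence.

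| | 0.1% | 1% |
|---|---|---|
| All enrolled (60) | 60 × 0.001 = 0.06 | 60 × 0.01 = 0.6 |
| Control arm (30) | 30 × 0.001 = 0.03 | 30 × 0.01 = 0.3 |

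This is fewer than one patient at either end of the range. The figures allow for no one being caught by dietitian, nurse, consent conversation or label, so they are upper figures for that assumed range.

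**The case against.** The case for leaving the text alone is substantial.

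- **Prior advice.** Entry requires that supplements have already been advised, with the number of bottles decided "fully in accordance with usual care" (6.5). Since supplements are usually dairy-based, a known milk allergy would usually have been noticed before screening.
- **Screening.** Soy allergy and lactose intolerance are themselves criteria, so the check must already touch on one food allergy and on dairy tolerance. That gives patient and dietitian an obvious occasion to mention a milk allergy.
- **Consent and product.** A conversation with the researcher and 24 hours or more for reflection come before randomisation (11.2). The products are not disguised: "patients will receive already existing products with standard packaging and labelling" (8.2).
- **Withdrawal.** A participant may leave at any time, and the investigator may withdraw someone for urgent medical reasons (8.4).

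All of this stands, and it makes the residual risk very small. It does not close the gap, because none of these steps is a written criterion on milk allergy, and withdrawal acts only after enrolment. Prior advice is also not proof that dairy is tolerated: section 6.4 says "Both types of ONS are already available and used in hospitals", so a clinician could have had the plant product in mind for such a patient. The protocol does not describe that practice; it is a possibility only.

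A reader might infer more than the document supports:

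- *That no allergy check is required at all.* Soy allergy is a criterion and must be checked.
- *That randomisation leaves the allergic patient no choice.* Consent, open labelling and free withdrawal leave one.
- *That patients receive no warning.* The patient information letter was not available for this review, so its content on ingredients is unknown.
- *That sections 4.3 and 13.2 contradict each other.* They share the same omission.

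**Conclusion.** The point holds as a gap in the listed criteria: milk-protein allergy is not named, there is no general exclusion for allergy to a product ingredient, and a patient with the known condition is therefore eligible. It is a low-priority safety improvement and does not amount to a design flaw. On an assumed prevalence of 0.1% to 1%, the expected number of such patients in the control arm is 0.03 to 0.3 before safeguards, and probably lower after them.

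The conclusion rests on two assumptions: that the control contains milk protein, which the protocol supports but does not state, and that the prevalence range is plausible, for which the protocol offers no evidence. The reading of the criteria depends on neither; only the practical consequence does.

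**What to change.** In section 4.3, change the dairy item to *Lactose intolerance or known cow's milk protein allergy*. Alternatively, add one criterion: *known allergy to any ingredient of either study product*. The second wording works whatever the control's protein source turns out to be.

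Mirror the change in section 13.2 and in the eligibility check of section 11.2, for both the dietitian route and the nurse and researcher route.

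The cost is one line in each place and on the eligibility form. The only downside is the exclusion of very few patients. The change protects only patients whose allergy is already known.

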#### **4.4 Sample size calculation**

We aim to enrol a convenience sample of 60 patients in this feasibility study, with n=30 per study group (i.e. plant-based vs animal-based ONS) which is deemed sufficient to answer the primary research question (21, 22).

If the results of this study show that the intervention can be considered feasible, future research with a fully powered sample size shall be performed to investigate the effect of the intervention on all parameters.

### **5. TREATMENT OF RESEARCH PARTICIPANTS**

#### **5.1 Investigational product/treatment**

Intervention product: plant-based ONS, Fresubin® Plant-based Drink vanilla. This will be compared to regular ONS, Fresubin® Yodrink raspberry with a similar nutritional content, i.e. 200ml, 300 kcal, 15 gram protein.

If the patient approves to participate in this study and signed the written IC then the patient will be randomised to one of the 2 groups: plant-based ONS or animal-based ONS.

#### **5.2 Use of co-intervention (if applicable)**

Not applicable

#### **5.3 Escape medication (if applicable)**

Not applicable

### **6. INVESTIGATIONAL PRODUCT**

#### **6.1 Name and description of investigational product(s)**

##### **6.1.1. Plant-based**

Investigational product is Fresubin® Plant-based Drink vanilla.

##### **6.1.2. Animal-based**

Control products is Fresubin® Yodrink raspberry.

Both types of ONS have the same nutritional content, i.e. 200ml, 300 kcal, 15 gram protein

#### **6.2 Summary of findings from non-clinical and studies**

Not applicable, there are no previous studies done with this plant-based ONS that is related to this research.

### **6.3 Summary of findings from clinical studies**

Not applicable, no previous studies with this plant-based ONS have been performed before.

### **6.4 Summary of known and potential risks and benefits**

There are no potential risks associated with this research. Patients will receive ONS as part of their regular treatment, however, with participating in this study they will be randomized to receive either the plant-based or animal-based ONS. Both types of ONS are already available and used in hospitals. Participating in this study has no specific additional benefit. Generally, the use of ONS is expected to increase the energy and protein intake for patients at risk for malnutrition, which in turn improves nutritional status.

### **6.5 Description and justification of route of administration and dosage**

The dietitian or nurse will decide the number of bottles the patient needs per day, fully in accordance with usual care. The advice of the dietitian or nurse needs to be at least 2 bottles ONS a day for patients to be eligible to participate in this study. This is based on their nutritional intake observed by the nurse or the dietitian will base this advice on their nutritional requirement at the start of their treatment. 2 bottles of ONS is equal to 600 kcal and 30g protein. This means that there need to be a gap between their intake and requirements of  $\geq 600$  kcal and  $\geq 30$  g protein, in order to advice the ONS. Nutritional requirements will be estimated for protein intake as 1.5-1.9 g/kg fat-free mass (FFM)/d and energy intake WHO formula + surcharge up to 50% according to the Dutch guidelines of malnutrition and the ESPEN guidelines Clinical nutrition in surgery, cancer, and geriatrics (6, 13, 23, 24).

If the patient approves to participate in this study and signed the written IC then the patient will be randomised to one of the 2 groups: plant-based ONS or animal-based ONS.

### **6.6 Dosages, dosage modifications and method of administration**

Dosage depends on advise of the dietitian or a nurse. This could be 2 bottles or more. Throughout the 3 months of the study, the advised amount of ONS may be adjusted to more or less bottles a day. This depends on their energy and protein intake and their requirements. Patients will record this advice in their logbook to ensure clarity to the researcher. The researcher will check this logbook with the patient.

## **7. NON-INVESTIGATIONAL PRODUCT**

Not applicable

- 7.1 Name and description of non-investigational product(s)**
- 7.2 Summary of findings from non-clinical studies**
- 7.3 Summary of findings from clinical studies**
- 7.4 Summary of known and potential risks and benefits**
- 7.5 Description and justification of route of administration and dosage**
- 7.6 Dosages, dosage modifications and method of administration**
- 7.7 Preparation and labelling of Non Investigational Medicinal Product**
- 7.8 Drug accountability**

## **8. METHODS**

### **8.1 Study parameters/endpoints**

#### **8.1.1 Main study parameter/endpoint**

The primary endpoint of the study is the feasibility (patient recruitment, drop-out rates, adherence, and study measurements) of a multicenter RNIT comparing plant-based and animal-based ONS in patients with cancer and lung diseases, cardiology patients, patients with cardiothoracic surgery, and orthopaedic patients at risk for an inadequate nutritional intake.

#### **8.1.2 Secondary study parameters/endpoints (if applicable)**

The secondary endpoints of this study is the energy and protein intake, nutritional status, muscle status, physical and clinical outcomes, and patient's satisfaction with long-term supplementation.

#### **8.1.3 Other study parameters (if applicable)**

Not applicable

### **8.2 Randomisation, blinding and treatment allocation**

Patients will be randomized to either the plant-based ONS or animal-based ONS. Randomisation will be done by Castor EDC database. This system will generate the randomisation performed by stratification for 3 different patient populations: (1) oncology, (2) pulmonary diseases (3) other (including cardiology, cardiothoracic surgery, orthopaedic patients) and for the study location (Radboudumc and Maastricht UMC+). In this way, it will be done independently. Patients can not be blinded in this study since it is

not feasible to cover every bottle the patients drink in those 3 months (i.e. patients will receive already existing products with standard packaging and labelling). Nevertheless, the analyses will be carried out in a blinded manner.

### 8.3 Study procedures

Measurements during this study will be combined as best as possible during appointments planned within routine care at the hospital. Baseline measurements will take place at the start of the ONS treatment (T0) during hospital admission or during an appointment at the outpatient clinic. 1 month after the start (T1) and 2 months after the start (T2) the researcher will have a brief 'check-in' via a phone call or a conversation at the hospital if the patient is there for another appointment. 3 months after initiation (T3) the same measurements will be performed as at baseline (T0). In addition, at T3, the researcher will conduct an interview about patients' satisfaction about the ONS (Table 1).

Table 1: Overview of the study measurements for each time point.

Measurements	Treatment initiation (T0)	1 month after initiation (T1)	2 months after initiation (T2)	3 months after initiation (T3)
Body height, body weight, usual body weight, BMI	X	X	X	X
Nutritional intake (protein and energy)	X			X
Compliance ONS	X	X	X	X
Check-in conversation		X	X	
Nutritional status (PG-SGA, fat mass and fat-free mass, and muscle thickness)	X			X

Hand grip strength	X			X
Physical Activity (SQUASH)	X			X
Physical performance (TUG, SPPB)	X			X
Quality of life (EORTC-QoL-C30) and Clinical outcome measures (length of hospital stay, complications, readmission and mortality)	X			X
Patient's satisfaction about the Oral nutritional supplements				X

Body height, body weight, BMI are measured on a calibrated scale and stadiometer. Usual body weight will be asked. During the check-in process, patients are required to weigh themselves either at home or at the hospital, if they have another appointment scheduled there.

Nutritional intake and compliance of oral nutritional supplements used during hospital admittance will be measured by food registration in the Electronic Patient Record (EPR) registered by the nutritional assistant with a cross-check of a nutritional researcher.

Additionally, the researcher will also ask if there are any variations in their food intake on bad versus good days and whether there have been any changes in eating habits compared to a month ago. Patients who are not admitted to hospital but come to the hospital on an outpatient basis, are being asked to fill out a 3-day food diary (2 week days and 1 weekend day). After 3 months the all patients will all fill out a 3-day food diary. During the 3 months,

participants will keep a logbook which they must record how much ONS was consumed daily for the total study period.

Individual protein requirement will be set at 1.5-1.9 g/kg FFM and energy requirements at WHO formula + surcharge up to 50% according to the Dutch guidelines of malnutrition and the ESPEN guidelines Clinical nutrition in surgery and cancer (6, 13, 23, 24).

For the check-in conversations the researcher will either make a phone call or have brief conversation at the hospital if the patient is already there for another appointment. The researcher will ask about any changes in body weight, discuss changes in the nutritional advice provided by the dietitian, their satisfaction about the ONS, ensure the patient is still correctly filling out the logbook, and address any questions or concerns related to the study.

Nutritional status will be measured by the Scored Patient-Generated Subjective Global Assessment (PG-SGA). The full PG-SGA has been validated among different patient groups and reported to be a simple instrument to use. Since the PG-SGA consists of a patient-reported part, the Dutch version of the PG-SGA will be used. This version is already available and considered comprehensible and easy to complete by patients, and comprehensible and relevant by professionals (20). One part is completed by the patient and another part by a specialist.

Body composition Fat mass (FM) and fat-free mass (FFM) will be measured using bioelectrical impedance analysis (BIA). The BIA device measures resistance in the body to an alternating current at 50kHz. FFM is then calculated with a formula that includes resistance, height, weight, sex and age. BIA represents a simple, non-invasive measure that takes only 5-10 min to perform.

Muscle thickness will be measured by muscle ultrasound with the Lumify (Philips) at the m. rectus femoris, vastus intermedius and m. biceps brachii.

Handgrip strength will be measured with the JAMAR handheld dynamometer in a standardized manner. Participants are asked to sit in an upward position with their elbows in a 90-degree angle and the wrist in a neutral position (thumb side upwards) and squeeze as hard as possible. Both hands will be measured 3 times, the highest value is used. Handgrip strength is a valid non-invasive method to measure muscle functionality and serves as a predictor for the overall muscle strength and change in nutritional status of participants.

Physical activity will be assessed using the questionnaire Short QUstionnaire to Assess Health-enhancing physical activity (SQUASH) at baseline and 3 months.

To measure Physical performance, the Short Physical Performance Battery (SPPB) and Timed Up and Go (TUG) will be used. The SPPB combines 3 separate tests, measuring gait speed, standing balance, and ability to rise from a chair. For the SPPB the scores of the 3 sub tests are all converted to a score range of 0-4, making the maximum score 12 points, indicating the best physical function (25). The TUG measures the time it takes for the patient to rise from a chair, walk comfortably 3 meters, turn around, walk back, and sit down. The patient may use their own walking aid and/or orthosis, but no physical assistance or encouragement should be given. This measurement is considered to be a reliable, cost-effective, safe, and time-efficient way to evaluate overall physical performance (26). The TUG and SPPB will be performed at baseline and 3 months.

Quality of Life will be evaluated using the EORTC-QoL-C30, a validated questionnaire for measuring quality of life. Questionnaires will be scored according to the procedures specified by the EORTC-QoL-C30 scoring manual (27).

Clinical outcome measures such as length of hospital stay, mortality and re-admissions within 3 months after hospital discharge will be determined retrospectively by using information from the EPR and confirmed by questionnaire with the participant since admissions from hospitals outside this study are not registered in an EPR. Complications within 3 months after hospital discharge will be determined by using information from the EPR. A complication is defined in line with the Dutch Association of Medical Specialists (FMS) as an unintended and undesirable event or condition during or following medical specialist intervention, which is so harmful to the health of the participant that change in medical treatment is necessary or that there is irreversible damage. Complications will be obtained from patients' medical records during hospital stay up to 3 months after baseline and coded as infectious, decubitus, surgical (non-infectious) complications and other (e.g., cardiopulmonary).

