### **10.2 Secondary study parameter(s)**

Secondary analysis will provide the mean difference in protein intake i.e., total protein intake in g/kg FFM/d (based on dietary history) divided by 1.5-1.9 g/kg FFM/d, times 100%. In addition, the mean difference in energy intake i.e., total energy intake in kcal/d (based on dietary history) divided by WHO formula + surcharge up to 50%, times 100%. ANCOVA analysis will be used to estimate the effect of the group as independent factor on 'mean difference in intake vs recommendation' at T3 as dependent variable and T0 measurement as covariate. This is only meant as exploratory analyses and to be used for sample size calculations for the subsequent full-scale RCT.

The aim of the semi-structured interviews is to understand the experiences and perspectives of the patients using ONS regarding satisfaction (taste, smell, satiety), as well as their wishes and needs. Additionally, we are interested in their views of

sustainable nutrition. Therefore, these interviews will be approached from a phenomenological perspective. Qualitative analysis: all interviews will be audiotaped, and the records will be transcribed verbatim. Data will be analyzed using thematic analysis, starting with initial open coding to identify relevant data by minimal two independently working researchers. Codes will then be grouped into categories, the axial codes, and overarching themes will be identified. For this analysis, the software Atlas.ti will be used.

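### Section 10.2 names a dietary history that section 8.3 does not collect, and the T0 intake covariate mixes two instruments with no indicator

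*Protocol*

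**What the plan says.** Section 10.2 defines two intake parameters, each expressed as a percentage of requirement. Protein uses "total protein intake in g/kg FFM/d (based on dietary history"; energy uses "total energy intake in kcal/d (based on dietary history) divided by WHO formula". The T3 value is then the outcome of an ANCOVA with group as factor and the T0 value as covariate. The section calls this exploratory and intends it for the sample size of the full trial.

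Section 8.3 says how intake is obtained:

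- **During admission:** intake "will be measured by food registration in the Electronic Patient Record (EPR) registered by the nutritional assistant", with a cross-check by a nutritional researcher. No number of recorded days is given.
- **Additional questions:** "the researcher will also ask if there are any variations in their food intake on bad versus good days", and about changes in eating habits over the past month.
- **Outpatients:** they "are being asked to fill out a 3-day food diary (2 week days and 1 weekend day").
- **At T3:** "After 3 months the all patients will all fill out a 3-day food diary".

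Section 8.3 also states that "3 months after initiation (T3) the same measurements will be performed as at baseline (T0"). Under section 8.2, randomisation is stratified by patient population and site, not by inpatient or outpatient start.

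**The concern.** Two things do not fit together. First, the analysis section names an intake source that the procedures section does not produce. The researcher's additional questions resemble part of a dietary history, but they supplement the registration and no conversion to grams or kilocalories is described.

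Second, the T0 value used for adjustment is a staff-kept hospital record in some patients and a self-kept diary in others. A systematic difference between the two adds variation to the T0 value that says nothing about a patient's intake at T3. The covariate then explains less of the T3 variance than it should. The correlation and residual variance estimated here would describe that mixture, and section 10.2 intends this analysis to inform the sample size of study 2.

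**Working it through.** **Instrument by setting and time (section 8.3)**

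| Start of study | T0 | T3 |
|---|---|---|
| Inpatient | EPR food registration, days not stated | 3-day diary |
| Outpatient | 3-day diary | 3-day diary |

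Neither row contains a dietary history. The T3 column has one instrument; the T0 column has two.

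**Size of the effect on the covariate.** The protocol gives no inpatient share, method difference, SD or correlation, so there is no figure to reproduce and every input below is an assumption. The method difference is taken as a constant shift, unrelated to a patient's true intake.

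- p = share starting as inpatients = 0.5
- d = method difference = 20 percentage points of requirement
- SD of true T0 intake = 25 points, so the variance is 625
- ρ = T0–T3 correlation with a single instrument = 0.50

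Step 1, added variance: p(1 − p)d² = 0.5 × 0.5 × 20² = 100. The T0 variance becomes 625 + 100 = 725, and the T0 SD becomes √725 = 26.9 instead of 25.

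Step 2, observed correlation: r = ρ√(625/725) = 0.50 × 0.928 = 0.464.

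Step 3, ANCOVA residual variance relative to a single-instrument covariate, which is also the ratio of required N: (1 − r²)/(1 − ρ²) = (1 − 0.2155)/(1 − 0.25) = 1.046, a rise of about 5%.

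**Range, with p = 0.5 and SD 25**

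| Rise in residual variance and N | ρ = 0.30 | ρ = 0.50 | ρ = 0.70 |
|---|---|---|---|
| d = 10 points (variance ratio 650/625 = 1.04) | 0.4% | 1.3% | 3.7% |
| d = 20 points (variance ratio 725/625 = 1.16) | 1.4% | 4.6% | 13.3% |

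With a difference of a full SD (25 points) the rise is 2%, 7% and 19% respectively.

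**Between-arm effect.** A simulation of the null ANCOVA used 30 patients per arm, ρ = 0.5, p = 0.5 and 5,000 runs. The mean group effect was −0.002, 0.000 and 0.003 SD for method differences of 0, 0.5 and 1.0 SD. The Monte Carlo standard error is about 0.23/√5000 = 0.003, so there is no sign of bias.

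**The case against.** The strongest reply is that little of consequence depends on this. Section 10.2 models the T3 value by group, so a reader who infers that the plan reports a biased T0–T3 change is criticising an analysis that no objective or research question asks for. Likewise, a reader might infer that the arms are compared with different instruments. They are not: everyone keeps the diary at T3. Because inpatient start is not a stratum, the T0 method mix can differ between arms by chance, but that does not bias the randomised comparison on average. Nor is the outcome SD for study 2 a mixture, since the T3 SD has a single source. All of this stands.

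It is also fair to say that no intake data are missing. Intake is collected at both times, and dietary history is a wrong label for it. The statement that T3 repeats the T0 measurements can be read as referring to the domains in Table 1; the same section openly gives the instrument for each setting. Hospital registration could not be repeated in patients who are at home by T3, and part of any hospital-to-home difference is real.

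Finally, the shift from 0.50 to 0.464 is small beside pilot noise. With 60 patients, the 95% Fisher interval around a correlation of 0.50 is about 0.28 to 0.67. With 30 in a subgroup it is about 0.17 to 0.73, which argues against planning study 2 from figures split by T0 method. Under the assumptions above, the error also makes study 2 somewhat larger, not smaller.

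What remains is that section 10.2 states the wrong source and fixes a model whose covariate sits on two scales. A later analysis plan could add a model term, but it might not be able to recover reliably the T0 method and the number of EPR days if these were not recorded at the time.

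**Conclusion.** The point holds as an inconsistency between sections 8.3 and 10.2 and as a modest weakness in the exploratory ANCOVA. The mixed covariate weakens the baseline adjustment and distorts the T0 SD, the T0–T3 correlation and the residual variance. It does not bias the between-arm comparison at T3 on average, and it leaves the T3 SD untouched.

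Under the assumed values the loss is about 5% in N. It is 1% or less where the correlation is low and the method difference small, and reaches 13% to 19% only with a correlation of 0.70 and a difference of 20 to 25 points. These figures rest on assumed inputs and on a constant shift; a difference in random error between the EPR record and the diary is not included.

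Any descriptive T0–T3 change in inpatients would mix change with method and setting, but the protocol plans no such analysis. This is a cheap improvement to a secondary analysis and does not threaten the feasibility objective.

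**What to change.** - In section 10.2, replace the reference to dietary history with the sources in section 8.3: EPR registration or 3-day diary at T0, and 3-day diary at T3.
- Record for each patient the T0 method (EPR or diary) and the number of EPR days used.
- Add T0 method as a term in the exploratory ANCOVA.
- Take the residual variance and T0–T3 correlation for study 2 from that adjusted model. They carry over only if study 2 uses one instrument at baseline or keeps the same term.
- Show results by T0 method descriptively only. If T0–T3 change is reported at all, show it by T0 method.

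The cost is a wording change, T0 method and EPR day count in the database, and one degree of freedom: with 60 patients and no drop-out, the residual degrees of freedom go from 57 to 56. The descriptive subgroup figures will be imprecise and should be labelled so. No visit or patient burden is added.
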